11.2 Definitions of Primary Endpoints and How These Will Be Analyzed

- 1) Proportion of objective tumor response as assessed by RECIST.
- 2) Frequency and severity of adverse events as assessed by CTCAE v4 and corresponding frequency table will be provided as descriptive statistics.

All patients who receive any therapy will be evaluated for both treatment efficacy and toxicity. Only those patients who are deemed "ineligible" or who receive no therapy will be eliminated from the analysis. While on occasion, circumstances may prevent the determination of treatment efficacy, such patients will be included in the analysis and labeled as "indeterminate." This category will be listed and be reflected in the calculation of the proportion responding.

11.3 Sample Size and Power Calculations:

The sample size and power calculations will be based on the optimal flexible two-stage method (24). This method assumes that the number of patients responding to the study regimen has binomial distribution and the accrual combination for stage 1 and 2 is uniformly distributed.

The minimum and maximum accruals for this study are 8 and 25 eligible and evaluable patients, respectively.

Under the assumed accrual ranges of 8 to 15 (stage 1) and 18 to 25 (cumulatively after stage 2), and under the rejection rules shown in **Table 8** for these accruals, the study has an average power of 90.0% at a target alpha=10% significance level to detect the 20% increase in the rate of tumor response from the null-hypothesis rate of 5% to a clinically interesting rate of 25% under the alternative hypothesis. The study's true alpha has an average of 9.5% with a 64.9% average probability of early termination and average expected sample size of 15.14 subjects under the null hypothesis.

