APPENDIX C- Specimen Shipping Instructions

1.0 OBJECTIVES

Primary Objectives & Hypothesis

Hypothesis: Because POLE/POLD1-ultramutated and/or hypermutated/MMR-defective endometrial tumors harbor a large number of novel mutations and are heavily infiltrated with TIL, anti-PD1 therapy with Pembrolizumab may represent an ideal treatment option for these patients to re-invigorate pre-existing immune responses and eliminate residual/recurrent chemotherapy and radiation resistant disease.

1.1 Primary Objectives:

- **1.1.1** To assess the antitumor activity (proportion of objective response by RECIST 1.1 criteria) of pembrolizumab with objective tumor response in patients with persistent, recurrent or metastatic endometrial cancer harboring an ultra-mutated or hyper-mutated (MMR gene-defective) phenotype identified by next generation sequencing (NGS) and comprehensive genomic profiling (CGP).
- **1.1.2** To determine the nature and degree of toxicity of pembrolizumab as assessed by CTCAE in patients with persistent, recurrent or metastatic endometrial carcinoma

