4.9 Subject Replacement Strategy

Early drop-outs and ineligible patients: If an enrolled subject drops out of the study before receiving treatment or is found to be ineligible, she will be replaced.

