4.10 Clinical Criteria for Early Trial Termination

Early trial termination will be the result of the criteria specified below:

- 1. Quality or quantity of data recording is inaccurate or incomplete
- 2. Poor adherence to protocol and regulatory requirements
- 3. Incidence or severity of adverse drug reaction in this or other studies indicates a potential health hazard to subjects
- 4. Plans to modify or discontinue the development of the study drug

In the event of Merck decision to no longer supply study drug, ample notification will be provided so that appropriate adjustments to subject treatment can be made.

If subject discontinues they will not be replaced.

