- d.) Unlikely: Adverse event is likely not to be related to the investigational procedures(s)/agent(s).
- e.) Unrelated: Adverse event is clearly not related to investigational procedures(s)/agent(s).

8.4 Plan for Grading Adverse Events:

The following scale will be used in grading the severity of adverse events noted during the study:

- 1. Mild adverse event
- 2. Moderate adverse event
- 3. Severe

8.5 Plan for Determining Seriousness of Adverse Events:

An adverse event may be graded as severe but still not meet the criteria for a Serious Adverse Event. Similarly, an adverse event may be graded as moderate but still meet the criteria for an SAE. It is important for the PI to consider the grade of the event as well as its "seriousness" when determining whether reporting to the IRB is necessary.

8.6 Plan for reporting Reportable Adverse Events and other unanticipated problems involving risks to subjects or others to the IRB

The principal investigator will report the following types of events to the IRB: a) adverse events that are serious or life-threatening AND unanticipated (or anticipated but occurring with a greater frequency than expected) AND possibly, probably or definitely related to the drug/device/intervention; and b) other unanticipated problems involving risks to subjects or others.

These adverse events or unanticipated problems involving risks to subjects or others will be reported to the IRB in accordance with IRB Policy 710, using the appropriate forms found on the website.

Plan for reporting adverse events to co-investigators on the study, as appropriate the protocol's research monitor(s), e.g., Yale Cancer Center Data and Safety Monitoring Committee (DSMC), Protocol Review Committee (PRC), DSMBs, study sponsors, funding and regulatory agencies, and regulatory and decision-making bodies.

For the current study, the following individuals, funding, and/or regulatory agencies will be notified (choose those that apply):

- X All Co-Investigators listed on the protocol.
- X Yale Cancer Center Data and Safety Monitoring Committee (DSMC)
- X Merck Pharmaceuticals

The principal investigator [name] will conduct a review of all adverse events upon completion of every study subject. The principal investigator will evaluate the frequency and severity of the adverse events and determine if modifications to the protocol or consent form are required.

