8.9 ASSESSMENT OF SAFETY

8.9.1 SPECIFICATION OF SAFETY VARIABLES

Safety assessments will consist of monitoring all adverse events and reporting adverse events (AEs) and serious adverse events (SAEs) that are considered related to **pembrolizumab**, all events of death, and any study specific issue of concern.

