10.4 Study Enrollment Procedures

Any modification of the original consent document provided to participating sites by the Coordinating Center must be approved in advance by the Coordinating Center. Rationale will be provided with any request for a change. A copy of each site's IRB and Coordinating Center approved informed consent document must be on file at the Gynecological Oncology Regulatory office before subjects may be enrolled.

To register eligible patients on this study, each site will contact the Multi-site Coordinator; [name] [contact]) or [name] [contact]) and provide the signed and dated eligibility checklist, completed signature page of the consent form and additional source documents if requested by the Principal Investigator or Multi-site Coordinator. Once the Principal Investigator or Multi-site Coordinator verifies eligibility, a unique subject study number will be issued. The subject will not be identified by name.

10.5 Responsibilities of the Lead Investigator [name]:

The lead investigator is responsible for the overall conduct of the study at all participating sites and for monitoring the safety and quality of the data as well as compliance to the protocol and with applicable federal regulations and Good Clinical Practice (GCP).

The lead investigator will monitor accrual rates at all sites for adequate progress.

The Lead Investigator will ensure appropriate coordination, submission and approval of the protocol as well as the consent documents and any subsequent amendments at all sites. There will be only one version of these documents that will be used by all participating institutions and the lead investigator is responsible for assuring that the correct versions are used by all participating institutions.

No additional sites will be added to the study without a proposed amendment and review and approval by the Yale IRB (HIC).

The lead investigator has the authority to suspend accrual at any site not complying with this protocol, including not submitting data in a timely manner. Any suspension of accrual will be reported to the Yale University Data Safety Monitoring Committee (DSMC) as well as to the Yale University HHRP. Site principal investigators must report the suspension to their IRB.

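### Section 11.2 does not limit the ineligibility exclusion to response, so a dosed patient later found ineligible can be left out of the primary adverse event table

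*Combined protocol and SAP*

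**What the plan says.** Section 11.2 covers both primary endpoints, the objective response proportion and the frequency and severity of adverse events. It sets the analysis population in two consecutive sentences: "All patients who receive any therapy will be evaluated for both treatment efficacy and toxicity", and then "Only those patients who are deemed 'ineligible' or who receive no therapy will be eliminated from the analysis". Patients whose response cannot be determined stay in the response denominator as indeterminate.

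Other sections that bear on the point:
- Sections 11.3 and 11.4 and Table 8 base the two-stage decision on eligible and evaluable patients, between 8 and 25 of them.
- Section 1.1.2 makes toxicity a primary objective: "To determine the nature and degree of toxicity of pembrolizumab as assessed by CTCAE in patients with persistent, recurrent or metastatic endometrial carcinoma".
- Section 8.9.1 states: "Safety assessments will consist of monitoring all adverse events". Under Section 8.6 the principal investigator "will conduct a review of all adverse events upon completion of every study subject". Section 11.4 has adverse events recorded on forms until the patient is off study therapy.
- Section 10.4 places an eligibility check at registration: "Once the Principal Investigator or Multi-site Coordinator verifies eligibility, a unique subject study number will be issued".
- Section 4.9 states: "If an enrolled subject drops out of the study before receiving treatment or is found to be ineligible, she will be replaced". Section 4.10 states: "If subject discontinues they will not be replaced".

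**The concern.** The exclusion sentence names ineligible patients separately from those who receive no therapy, so the first group can include women who were dosed. It follows directly on a sentence that names both efficacy and toxicity, and it removes them from the analysis without saying which one. An analyst who follows the text could therefore drop a dosed patient from the adverse event table as well as from the response proportion.

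Dropping her from the response decision fits the design. Dropping her from the toxicity table does not serve that endpoint: she was exposed to the drug, and her events bear on its toxicity whether or not she met every entry criterion. With at most 25 patients, each one is at least 1/25 = 4% of the table.

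For response, the plan does not require an all-treated proportion. If late exclusions occur in this open-label trial, a reader cannot see what difference they made.

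**Working it through.** **1. The plan's own design figures.** Inputs from Section 11.3 and Table 8: stage 1 size n1 = 8–15 and cumulative size n2 = 18–25, with the 64 pairs equally weighted. Stop at stage 1 with 0 responses of 8–13, or at most 1 of 14–15. Reject the regimen at the end with at most 1 of 18, or at most 2 of 19–25. Response rates are 5% (null) and 25% (alternative).

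For each pair, with stage 1 cut-off a1 and final cut-off a2:
- P(early stop) = P(X1 ≤ a1), with X1 ~ Bin(n1, p).
- P(declared interesting) = sum over x > a1 of P(X1 = x) × P(X2 ≥ a2 + 1 − x), with X2 ~ Bin(n2 − n1, p).
- Expected N = n1 × P(early stop) + n2 × (1 − P(early stop)).

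| Average over 64 pairs | Stated | Recomputed |
|---|---|---|
| Power at 25% | 90.0% | 0.9005 |
| Alpha at 5% | 9.5% | 0.0945 |
| Early termination at 5% | 64.9% | 0.649 |
| Expected N at 5% | 15.14 | 15.13 |

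The design reproduces. All these figures refer to eligible and evaluable patients, so changing the population of the adverse event table leaves them as they are.

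**2. The text, for a patient dosed and later found ineligible.**
- The first sentence of Section 11.2 on populations includes her for efficacy and toxicity.
- The second removes her from the analysis, with no limit to response.
- Sections 8.6, 8.9.1 and 11.4 cover collection, monitoring and review of her events. None of them says who enters the Section 11.2 table.

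No other section resolves the conflict between the two sentences.

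**3. Size for toxicity.** The documents give no number of dosed but ineligible patients. Assume one, with 22 eligible patients (the Section 11.3 and 11.4 target), so 23 dosed. Suppose an event type occurs only in her.
- All dosed: 1/23 = 4.3%. Clopper–Pearson lower limit 1 − 0.975^(1/23) = 0.1%; upper limit is the 97.5% point of Beta(2, 22) = 21.9%.
- With her excluded: 0/22 = 0%. Upper limit 1 − 0.025^(1/22) = 15.4%.

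Given that one such exclusion happens, and with a true event rate a, the chance that it hides a given event type completely is a × (1 − a)^22:
- a = 2%: 0.02 × 0.98^22 = 1.3%
- a = 5%: 0.05 × 0.95^22 = 1.6%
- a = 10%: 0.10 × 0.90^22 = 1.0%

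If she did not have the event, her removal moves the rate the other way; for example, 2/23 = 8.7% becomes 2/22 = 9.1%.

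**4. Size for response.** Suppose 3 responders among the 22 eligible patients and a non-response in the excluded one. The eligible set gives 3/22 = 13.6% and the all-treated set 3/23 = 13.0%. The Table 8 cut-off is 2 at both 22 and 23, so the decision is the same.

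**The case against.** The best defence is that Section 11.2 already includes all treated patients for toxicity, and that the sentences after the exclusion concern efficacy and the proportion responding. On that view the exclusion refers to the response analysis alone. This is a fair reading, and it may be what was intended. It does not remove the problem, because the exclusion sentence has no such limit and no safety population is named elsewhere.

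Four further readings are tempting, and the documents do not support them.

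- **Safety data would be lost.** They would not. Sections 8.6, 8.9.1 and 11.4 keep her events recorded, monitored and reviewed. The gap is in one table's denominator and can be repaired at analysis.
- **The exclusion inflates the false-positive rate.** With replacement, that needs known non-responders to be removed because of their outcome, and nothing in the documents suggests such conduct. Without replacement, moving the final count from 19 to 18 lowers the Table 8 cut-off from 2 to 1. That step belongs to Table 8: with nobody excluded, exact alpha at a 5% response rate is 6.5% at sizes 12/19 and 20.9% at 12/18, both permitted pairs. It is not evidence against Section 11.2.
- **Objective 1.1.2 deliberately covers patients without the mutation phenotype.** Its wording does omit the restriction, but Sections 3.1 and 3.2.3 restrict the whole trial. Section 3.2.3 also accepts sequencing and/or standard MSI and IHC testing, so a discordant second test does not by itself make a patient ineligible.
- **Sections 4.9 and 4.10 leave replacement undefined.** Section 4.9 is the dedicated replacement rule and names patients found ineligible; Section 4.10 makes a general remark about subjects who discontinue. A cross-reference would be tidier, but little depends on it.

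The defence is right about scale. Eligibility is verified before a study number is issued, so late findings should be few. Basing the decision on eligible patients is legitimate, and keeping indeterminate patients in the denominator already deals with the commoner source of inflation.

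**Conclusion.** The point holds as a minor defect of wording in a primary analysis. As written, Section 11.2 can leave a dosed patient later found ineligible out of the primary adverse event table, and it requires no all-treated response proportion. It does not show a failure of safety monitoring or a fault in the two-stage design.

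The size rests on an assumed single exclusion from 23 dosed patients, because the documents give no rate. In that illustration an event seen only in her reads 0/22 instead of 1/23, and 3 responders read as 13.6% instead of 13.0%. More late exclusions would widen these gaps; with none, there is no effect.

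**What to change.** - **(a)** Reword Section 11.2 so that the ineligibility exclusion applies only to the response decision. Tabulate adverse events in every patient who received at least one dose, whatever her eligibility.
- **(b)** Keep the eligible and evaluable set for Table 8. Report the all-treated response proportion beside it as supportive, and list each dosed patient excluded as ineligible with the reason.

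Optional: add a line to Section 4.9 or 4.10 saying which governs a dosed patient found ineligible, and state that a late ineligibility call rests on pre-treatment data and is made without reference to response.

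Cost: a short amendment, since Section 11 is part of the protocol, plus one extra proportion and a brief listing. The extra proportion may be slightly lower than the eligible one. Table 8 and the stated operating characteristics stay as they are. Items (a) and (b) use data already collected and can be applied at analysis even if accrual has closed, which the documents do not state.

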11.4 Study Monitoring of Primary Objectives

There will be one formal futility interim analysis for treatment efficacy in the study.

If the study has an accrual of 12 eligible and evaluable patients in the first stage since the study is activated, which is permitted to range from 8 to 15, the accrual of the study will be temporarily suspended until the data of primary endpoint is matured to make a decision on whether to go forward to second stage accrual according to the guidelines. That is, if there are 0 out of 8-13 or at most 1 out of 14-15 patients responding (complete or partial response) and medical judgment indicates, the study will be stopped and the treatment will be classified as clinically uninteresting. Otherwise, accrual to the second stage of the trial will be initiated. As this is a two-stage multi-institutional phase II protocol, the initial overall review of toxicity is usually performed after completion of the first stage of accrual, at which point accrual is generally suspended pending formal analysis of response.

Accrual Goal

The projected minimum and maximum accruals for the study are 8 and 25 eligible and evaluable patients, respectively. The targeted accrual is 12 eligible and evaluable patients in the first stage of the study, and cumulatively 22 eligible and evaluable patients will be targeted in the second stage if the study advances.

Study Duration

1) Patients will receive therapy until disease progression or intolerable toxicity intervenes.

The patient can refuse the study treatment at any time.

2) All patients will be treated (with completion of all required case report forms) until disease progression, initiation of a subsequent cancer treatment or study withdrawal.

Patients will then be followed every three months for the first two years and then every six months for the next three years.

3) A patient is considered off study therapy when the patient has progressed or died, a nonprotocol drug or therapy (directed at the disease) is initiated, or all study therapy is discontinued. Report all treatment received on Cycle Drug Information Forms and adverse events on Adverse Events Forms until the patient qualifies as being off study therapy.

Estimated Duration for Completion of Primary Endpoint: provision of timeframe, e.g. 24 months from activation

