Treatment Toxicity: The grade level of the various toxicities will be classified using the Common Toxicity Criteria, version 4 (CTC, v.4) guidelines. Acute toxicities will be scored if occurring </= 30 days from treatment completion, and chronic if > 30 days. Frequency and duration of treatment interruptions due to the treatment toxicity will be assessed.

8.0 STUDY MONITORING AND REPORTING PROCEDURES

8.1 Personnel responsible for the safety review and its frequency:

The principal investigator will be responsible for monitoring the data, assuring protocol compliance, and conducting the safety reviews at the specified frequency which must be conducted at a minimum of every 6 months (including when reapproval of the protocol is sought). During the review process, the principal

investigator with the help of the Remote Monitoring Coordinator will evaluate whether the study should continue unchanged, require modification/amendment, or close to enrollment. Either the principal investigator, the IRB or the Yale Cancer Center Data and Safety Monitoring Committee (DSMC) have the authority to stop or suspend the study or require modifications.

8.2 The risks associated with the current study are deemed moderate for the following reasons:

- 1. We do not view the risks associated with pembrolizumab as minimal.
- 2. Given the now established safety and validity of studies performed using the FDA-approved drug pembrolizumab, we do not view the proposed study as high risk.

Although we have assessed the proposed study as one of moderate risk, the potential exists for anticipated and/or unanticipated adverse events, serious or otherwise, to occur since it is not possible to predict with certainty the absolute risk in any given individual or in advance of first-hand experience with the proposed study methods. Therefore, we provide a plan for monitoring the data and safety of the proposed study as follows:

8.3 Attribution of Adverse Events:

Adverse events will be monitored for each subject participating in the study and attributed to the study procedures / design by the principal investigator [name], according to the following categories:

a.) Definite: Adverse event is clearly related to investigational procedures(s)/agent(s).

- b.) Probable: Adverse event is likely related to investigational procedures(s)/agent(s).
- c.) Possible: Adverse event may be related to investigational procedures(s)/agent(s).

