11 STATISTICAL ANALYSIS PLAN

a. Statistical Analysis Plan

This is a single-arm, open-label phase II study using the optimal flexible two-stage design of Chen *et al.* (24) to evaluate the efficacy of the study regimen through objective tumor response. There are no treatment comparisons involved and no known historical controls available.

The targeted accrual for the first stage of the study will be 12 eligible and evaluable patients but permitted to range from 8 to 15 for administrative reasons. The cumulative targeted accrual for the second stage will be 22 eligible and evaluable patients but permitted to range from 18 to 25 for administrative reasons.

If the true probability of tumor response is 5%, then the study has a 65% average probability of early termination and an expected probability of 10% of incorrectly declaring the study regimen interesting. If the true probability of tumor response is 25%, then the study has an expected 90% chance of correctly classifying the study regimen as being interesting.

11.0 Justification of Design:

This study will employ the optimal flexible two-stage design since it not only minimizes the average expected number of patient exposure to inactive regimen, but also allows the actual study accrual to slightly deviate from the targeted study accrual in a multi-center trial while maintaining the levels of the average type I and II errors.

Study Endpoints

11.1Primary Endpoints

1) Frequency of objective tumor response as assessed by RECIST. Subjects who continue treatment beyond initial investigator-assessed, RECIST 1.1-defined progression will be considered to have investigator-assessed progressive disease at the time of the initial progression event but may be designated as delayed responses for purposes of determining proportion of objective response and counted as responses for two stage designs.

2) Frequency and severity of adverse events as assessed by CTCAE v4.

Secondary Endpoints

1) Duration of progression-free survival (PFS) and overall survival (OS).

Translational Science Objectives

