We will target an accrual of 12 eligible and evaluable patients in the first stage of the study, but permit the accrual to range from 8 to 15 for administration reasons. If there are more than 0 out of 8-13 or 1 out of 14-15 patients responding (complete or partial response) and medical judgment indicates, accrual to the second stage of the trial will be initiated. Otherwise, the study will be stopped and the treatment will be classified as clinically uninteresting. If the study advances to the second stage, then a cumulative accrual of 22 eligible and evaluable patients will be targeted, but permitted to range from 18 to 25 for administration reasons. If more than 1 out 18, or 2 out 19-25 patients respond and medical judgment indicates, then the study regimen will be considered worthy for further investigation.

Under the assumed accrual ranges of 8 to 15 (stage 1) and 18 to 25 (cumulatively after stage 2), and under the rejection rules associated with these accrual ranges, if the true probability of tumor response is 5%, then the study has a 65% average probability of early termination and an average 10% probability of incorrectly declaring the study regimen interesting; if the true probability of tumor response is 25%, then the study has a 90% average chance of correctly classifying the study regimen as being interesting.

Table 8: Accrual Ranges and Associated Rejection Rules.					
Stage of Accrual	Targeted Cumulative Accrual	Limits of Actual Accrual	Max Number of Responses to Reject Study Regimen		
1	12	8-15	0/(8-13), 1/14-15		
2	22	18-25	1/(18), 2/(19-25)		

The following table (Table 8) summarizes the accrual ranges and associated rejection rules.

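### Sections 11.1 and 11.4 give opposite interim decisions when medical judgment and the response count disagree, and the stated operating characteristics belong to a count-only rule that neither section describes

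*Combined protocol and SAP*

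**What the plan says.** The interim rule is given twice.

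- The text under Primary Hypothesis (between headings 11.1 and 11.2, called 11.1 here) requires a count above the limit "and medical judgment indicates, accrual to the second stage of the trial will be initiated. Otherwise, the study will be stopped".
- Section 11.4 requires a count at or below the limit before stopping. For stage 1 sizes of 14 or 15 it reads "at most 1 out of 14-15 patients responding (complete or partial response) and medical judgment indicates, the study will be stopped". The default follows: "Otherwise, accrual to the second stage of the trial will be initiated".

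The final decision in 11.1 also depends on judgment: if enough "patients respond and medical judgment indicates, then the study regimen will be considered worthy for further investigation". Table 8 contains counts only.

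Section 11.3 reports that the "true alpha has an average of 9.5% with a 64.9% average probability of early termination", with an average expected sample size of 15.14 under the null and average power of 90.0%. Section 11.0 justifies the design because "it not only minimizes the average expected number of patient exposure to inactive regimen".

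**The concern.** Each section sets two conditions for its own action and makes the opposite action the default. When count and judgment disagree, in either direction, 11.1 stops and 11.4 continues. Nothing in the plan says which text governs or whether the limit is binding.

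This is the only formal interim analysis, and the stage 1 stop is what limits exposure to an inactive regimen. The case with most practical effect is a failed count with judgment in favour of continuing. That is plausible here, because the primary endpoint definition in 11.1 allows responses after initial RECIST progression to count as delayed responses in the two-stage rule. A low stage 1 count with late responses still possible is where an investigator might want to go on. Under 11.4 that is allowed; under 11.1 it is not.

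**Working it through.** **The two rules side by side**

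| Stage 1 count | Medical judgment | 11.1 | 11.4 |
|---|---|---|---|
| above limit | continue | stage 2 | stage 2 |
| above limit | stop | stop | stage 2 |
| at or below limit | continue | stop | stage 2 |
| at or below limit | stop | stop | stop |

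The sections agree only in the first and last rows.

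**Inputs**

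- Response rates, 11.3: "from the null-hypothesis rate of 5% to a clinically interesting rate of 25% under the alternative hypothesis".
- Accrual, 11.3: stage 1 n1 = 8 to 15, cumulative n2 = 18 to 25, all 8 × 8 = 64 pairs weighted equally.
- Limits, Table 8: r1 = 0 for n1 = 8–13 and 1 for n1 = 14–15; r2 = 1 for n2 = 18 and 2 for n2 = 19–25.

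**Formulas for one pair, counts binding**

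- Early termination: PET = P(X1 ≤ r1), X1 ~ Bin(n1, p).
- Declared interesting: sum over x > r1 of P(X1 = x) × P(X2 ≥ r2 + 1 − x), X2 ~ Bin(n2 − n1, p).
- Expected size: EN = n1 × PET + n2 × (1 − PET).

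**Reproducing the plan's figures**

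At p = 0.05, PET for n1 = 8 to 15 is 0.6634, 0.6302, 0.5987, 0.5688, 0.5404, 0.5133, 0.8470, 0.8290. The mean is 5.1908 / 8 = 0.649.

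| | Recomputed | Stated in 11.3 |
|---|---|---|
| Early termination, p = 0.05 | 64.89% | 64.9% |
| Average alpha | 9.45% | 9.5% |
| Expected size, p = 0.05 | 15.13 | 15.14 |
| Average power, p = 0.25 | 90.05% | 90.0% |

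The stated figures are correct for the count rule with no discretion.

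**Overrides allowed by 11.4**

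Let q be the share of count-based stops that judgment overrides (an assumption). With every stop overridden, only the final limit applies: average alpha is 11.21%, EN is the mean of 18 to 25 = 21.50, and power is 93.8%. For other q, under the null:

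- PET = 0.6489 × (1 − q)
- EN = 15.13 + q × (21.50 − 15.13)
- alpha = 0.0945 + q × (0.1121 − 0.0945)

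| q | PET | EN | Average alpha |
|---|---|---|---|
| 0 | 64.9% | 15.1 | 9.5% |
| 10% | 58.4% | 15.8 | 9.6% |
| 25% | 48.7% | 16.7 | 9.9% |
| 50% | 32.4% | 18.3 | 10.3% |
| 100% | 0% | 21.5 | 11.2% |

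- Average alpha reaches the 10% target at q of about 31%.
- Each overridden stop adds (21.50 − 15.13) / 0.6489 = 9.8 patients on average.
- The final judgment condition can only lower alpha. With q = 100% and 11% of final successes vetoed, alpha is 0.1121 × 0.89 = 9.97%.
- At the targeted 12 and 22 patients, going from q = 0 to q = 100% moves PET from 0.95^12 = 54.0% to 0%, EN from 12 × 0.540 + 22 × 0.460 = 16.6 to 22.0, and alpha from 8.9% to 9.5%.

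**Vetoes allowed by 11.1**

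If a share v of passed interims is vetoed (also an assumption), power is 0.9005 × (1 − v) and alpha is 0.0945 × (1 − v). At v = 5%, power is 85.5% and alpha 9.0%. At v = 10%, they are 81.0% and 8.5%.

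**The case against.** The best defence is that 11.4 only restates the rule: it says the decision follows the guidelines and introduces the stopping sentence as an explanation of them. On that reading the inverted condition is loose drafting, and no override was planned. This makes an intended override less likely, but it leaves two texts with different actions and does not say which governs.

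Section 11.3 also ties its figures to the Table 8 rules, so a careful reader can tell that they are count-based. They hold as well if judgment always follows the count, which is the same rule in practice. That is fair: the figures are not miscalculated. The fault lies in the decision text around them.

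The sizes rest on assumed rates. At 10% overridden, expected size rises only from 15.1 to 15.8. At a true response rate of 25%, a count-based stop occurs in only 6.4% of trials on average (3.2% at the 12-patient target), so overrides matter mainly when the drug is nearly inactive. These limits stand.

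For a passed count with judgment against continuing, section 8.1 already says that the principal investigator, the IRB or the DSMC "have the authority to stop or suspend the study or require modifications". That covers part of the veto case but does not settle whether a failed stage 1 may continue.

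Finally, the trial summary has the study ending in June 2020 and the text is Version 9.0 of April 2023, so the interim has probably passed, although the documents do not confirm it. The rule actually applied would still need to be stated, because the design's reported properties depend on it.

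**Conclusion.** The concern holds. Sections 11.1 and 11.4 prescribe opposite actions in both cases where count and judgment disagree. The figures in 11.3 describe the count rule without discretion; 11.4 lets a failed stage 1 be overridden, and 11.1 lets a passed one be vetoed.

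The effect falls mainly on early stopping and expected sample size under the null, and how large it is depends on override rates that the plan does not give. The effect on type I error is minor: average alpha exceeds 10% only above about 31% overridden, and it stays below 10% at the 12/22 target even if every stop is overridden. The wording should be corrected; sample size, Table 8 and the reported figures need no change.

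**What to change.** Use one rule in both places. Section 11.1 and Table 8 can stay.

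1. In 11.4, remove the medical-judgment condition from the stopping sentence, so that a stage 1 count at or below the Table 8 limit stops the study (binding).
2. In 11.4, replace the default sentence with one that matches 11.1: above the limit, stage 2 opens unless medical judgment is against it, in which case the study stops.
3. In 11.3, add that the reported figures are for the count rule alone, and that a judgment veto at the interim or the final stage can only lower alpha and power.

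If the interim decision has already been taken, also record which rule was applied.

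The cost is two sentences in 11.4 and one in 11.3. The study gives up the discretion to continue after a failed stage 1, which its stated error rates already exclude. The retained veto costs about 4.5 points of power for every 5% of passed interims vetoed (0.05 × 90.05%), and the added sentence tells the reader that vetoes lower power.
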